# 7 Statistical Plan

## 7.1 Statistical Methods

This is a first-in-humans pilot study/Phase I trial designed to (1) test the safety and toxicity of the OxyChip and patient tolerance of its presence and to (2) help design a larger confirmatory study. As such, the study was sequentially designed into different cohorts, as previously described in section\_3.1. The criteria for proceeding with each cohort is not based on statistical significance but on the presence and severity of any unexpected adverse events and whether they can be attributed to the OxyChip. The sample size was selected to be within the range recommended for early phase I trials.

For purposes of examining the secondary goal, the feasibility of using the OxyChip to assess PO2, we will use a qualitative assessment about whether any attempted measurements were successful, and assess the time for making measurements. Oxygen measurements will be averaged across visit days (if available) per subject for all subjects in Phase 1A and Phase 1B. We will use a paired t-test to detect statistically significant acute changes in pO2. To compare time period measurements per visit across patients, we will use an ANOVA model to account for individual variation of the baseline pO2. Finally, if the oxygen level exhibits a nonlinear pattern we will use a nonlinear fitting technique. To account for substantial variations of pO2 across patients, methods of repeated measurements and mixed modeling will be used.

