## Study Summary

Title	A Single-Institutional, Phase I Trial of Repeated Oxygen Measurements in Subcutaneous Tumors by Electron Paramagnetic Resonance (EPR) Oximetry using an Implantable Oxygen Sensor (OxyChip)
Short Title	EPR Oximetry using OxyChip
Protocol Number	D14007, CPHS 28499
Phase	First-in-humans, early feasibility study for OxyChip implantation with subsequent expansion to a larger Phase I trial. Phases: 1A (tumor with planned surgical resection only and consequently with an expected duration of implantation for up to 4 weeks); and 1B (tumor with neoadjuvant radiation therapy or chemotherapy followed by planned surgical resection, with expected duration of implantation of up to 12 weeks for radiation and 24 weeks or more for chemotherapy.) OxyChip implant duration for both phases can be extended to 52 weeks excluding the first 6 patients enrolled into Phase 1A where implant duration is up to 4 weeks.
Methodology	Phase I (first-in-human, early feasibility trial)
Study Duration	5 years
Study Center(s)	Single institution: Dartmouth-Hitchcock Medical Center (DHMC)
Objectives	Primary: Establishment of safety of OxyChip implantation in humans; Secondary: establishment of feasibility of OxyChip for measurements of oxygen using EPR oximetry in humans.
Number of Subjects	60 total evaluable subjects planned: 3 subjects in Phase1A will be evaluated and reviewed before enrolling another 3 subjects. After completion of the first 6 subjects in Phase 1A, if there are no unacceptable toxicities from the OxyChip, that cohort will be expanded to a total of 30 subjects. Phase 1B will consist of one cohort of 3 subjects receiving chemotherapy and one cohort of 3 subjects receiving radiotherapy. Once a cohort has enrolled 3 subjects and there are no unacceptable toxicities from the OxyChip, the completed cohort will be expanded to enroll additional subjects. No more than 30 subjects will be enrolled in Phase 1B. Phase 1A and Phase 1B will be evaluated separately with regards to this expansion; i.e. , Phase 1A may expand to 30 subjects while Phase 1B is still accruing.
Diagnosis and Main Inclusion Criteria	Tumors, located within 3 cm of skin or mucosal surface AND tumor resection is planned.

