The resected tissues showed no signs of infection. There was evidence of an inflammatory response associated with expected trauma along the needle track from the implantation itself. In a few patients, a typical foreign body reaction was evident. As graded by the pathologist ([name]) no findings indicative of significant, clinically concerning inflammation or reaction were found in any patient. In addition, via clinician assessment, no patients had any significant clinical toxicity associated with the implantation procedure or the presence of the OxyChip itself. The maximum CTCAE toxicity grade was 1.0.

Phase 1A and 1B still require removal of the OxyChip . However, it is important to note that based on the above safety data the FDA has now given permission to proceed with evaluation of permanent implantation of the OxyChip.

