## 2 Study Objectives

### 2.1 Primary Objective

This is a safety study to demonstrate that the implantation procedure, the OxyChip, and any subsequent oxygen measurements will be well-tolerated by the patient with minimal risk for complications. Specific adverse effects that will be monitored include:

- Allergic reactions or signs of inflammation at the site of implantation or systemically
- Infection at the site of implantation
- Bleeding at the site of implantation
- All tumors will be excised with the OxyChip in place, and histology will be analyzed for signs of tissue reaction and inflammation adjacent to the OxyChip
- Device (PDMS-embedded) breakage, loss of EPR or oxygen sensitivity, or change of calibration
- Erosion of skin over the implantation site
- Any unanticipated adverse device effects (UADE) will be assessed and reported. UADE will be defined as, “any serious adverse effect on health or safety or any life-threatening problem or death caused by, or associated with, a device, if that effect, problem, or death was not previously identified in nature, severity, or degree of incidence in the investigational plan or application, or any other unanticipated serious problem associated with a device that relates to the rights, safety, or welfare of subjects” (21 CFR 812.3(s)).

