### 3.2 Primary Study Endpoint

For the primary objective (*safety of the implantation procedure: the OxyChip itself and removal of the OxyChip is expected to be well-tolerated with minimal risk for complications*). The primary endpoints will be

all grade 3 or higher toxicities according to the Common Terminology Criteria for Adverse Effects (CTCAE) that are attributed to the device or procedure.

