## 8 Safety and Adverse Events

### 8.1 Definitions

#### 8.1.1 Adverse event definitions

**Adverse effect.** Any untoward medical occurrence in a clinical study of an investigational device; regardless of the causal relationship of the problem with the device or, if applicable, other study treatment or diagnostic product(s).

**Associated with the investigational device or, if applicable, other study treatment or diagnostic product(s).** There is a reasonable possibility that the adverse effect may have been caused by the investigational device or, if applicable, the other study treatment or diagnostic product(s).

**Disability.** A substantial disruption of a person's ability to conduct normal life functions.

**Life-threatening adverse effect.** Any adverse effect that places the subject, in the view of the investigator-sponsor, at immediate risk of death from the effect as it occurred (i.e., does not include an adverse effect that, had it actually occurred in a more severe form, might have caused death).

**Serious adverse effect.** Any adverse effect that results in any of the following outcomes: death, a life-threatening adverse effect, inpatient hospitalization or prolongation of existing hospitalization, a persistent or significant disability/incapacity, or a congenital anomaly/birth defect.

- **Hospitalization** shall include any initial admission (even if less than 24 hours) to a healthcare facility as a result of a precipitating clinical adverse effect; to include transfer within the hospital to an intensive care unit. Hospitalization or prolongation of hospitalization in the absence of a precipitating, clinical adverse effect (e.g., for a preexisting condition not associated with a new adverse effect or with a worsening of the preexisting condition; admission for a protocol-specified procedure) is not, in itself, a serious adverse effect.

**Unexpected adverse effect.** Any adverse effect, the frequency, specificity or severity of which is not consistent with the risk information described in the clinical study protocol(s) or elsewhere in the current IDE application, as amended.

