### **8.4 Stopping Rules**

The study will be stopped for any grade 3 or higher toxicity. The study will not re-open until the event is analyzed and deemed to be unrelated to the OxyChip or oxygen measurements.

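### The 8.4 re-opening test and the 7.1 progression criterion do not use the attribution in the 3.2 primary endpoint (device or procedure), so the study could re-open after a procedure-caused primary-endpoint event

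*Combined protocol and SAP*

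**What the plan says.** Section 3.2 counts CTCAE grade 3+ toxicities "that are attributed to the device or procedure". Its objective line reads "safety of the implantation procedure: the OxyChip itself and removal of the OxyChip is expected to be well-tolerated", so implantation and removal are both within scope. Section 2.1 sets out to show that "the implantation procedure, the OxyChip, and any subsequent oxygen measurements will be well-tolerated by the patient".

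Section 7.1 says that moving from one cohort to the next depends not on statistical significance "but on the presence and severity of any unexpected adverse events and whether they can be attributed to the OxyChip".

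Section 8.4 halts the study for any grade 3+ toxicity, whatever its cause, and then adds: "The study will not re-open until the event is analyzed and deemed to be unrelated to the OxyChip or oxygen measurements".

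The Study Summary states the Phase 1B expansion condition as "Once a cohort has enrolled 3 subjects and there are no unacceptable toxicities from the OxyChip".

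**The concern.** In a first-in-human safety study, the rules for continuing should respond to the same events that the primary endpoint counts. Here they do not. The endpoint covers harm from the procedure. The progression criterion and the re-opening test name the chip, and in 8.4 also the measurements, but neither names placement or removal.

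Placement is the invasive step that the study adds to routine care. Section 5.2.1 now expects fiducials in most tumors, loaded in the same needle as the chip. Section 1.6.1 plans to train further investigators in the injection. If the needle or a fiducial caused a serious bleed or infection, the written re-opening test could be met by the finding that the chip was not to blame.

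**Working it through.** No arithmetic applies to the rules themselves, because the plan gives no event rate, error rate or power for its gates. The check is to set the wordings side by side and follow one event through them.

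| Place | Events considered | Attribution required |
|---|---|---|
| 3.2 primary endpoint | Grade 3+ | Device or procedure |
| 8.4 stop | Grade 3+ | None |
| 8.4 re-opening | The event that caused the stop | Chip or oxygen measurements |
| 7.1 progression | Unexpected, any grade | Chip |
| Study Summary, expansion of 1A and 1B | Unacceptable toxicities | Chip |
| 3.1, Phase 1A after six patients | Unacceptable toxicity; chip must be implanted and removed successfully | None |
| 3.1 schema, Phase 1A after three patients | Any adverse event on examination or pathology | None |
| 1.6.1, Phase 1A expansion | Unacceptable toxicities, including UADEs | None |
| 3.1 schema, Phase 1B | Full evaluation of three patients; the PI decides after pathology review and more than 2 weeks after removal | No toxicity criterion stated |

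**Tracing a grade 3 bleed caused by the placement needle.**
1. Under 3.2 it is a primary-endpoint event, because it is attributed to the procedure.
2. Under 8.4 the study stops.
3. Under the 8.4 re-opening test, neither the chip nor the measurements caused it. Read literally, the test is met.
4. Under 7.1 it must first be unexpected. Section 1.7 lists bleeding as a known risk, but the definition in 8.1.1 takes in severity beyond the described risk. With the risk described as minimal, a grade 3 bleed would probably qualify. It must then be attributable to the OxyChip, and read literally it is not.

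So 7.1 is narrower than 3.2 on attribution and, less firmly, on expectedness. It is not narrower on grade, since it has no grade 3 floor.

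**Does the bare word OxyChip include putting it in?** Section 1.2 defines the OxyChip as a small cylindrical piece of material. Section 3.2 separates device from procedure. Section 2.1 lists procedure, chip and measurements as three items. The progress report in Section 1.5 describes toxicity "associated with the implantation procedure or the presence of the OxyChip itself", which again treats them as two things. Section 8.4 itself lists the measurements apart from the chip. A fiducial is not an OxyChip on any reading.

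**Study-specific removal.** Removal normally happens in the planned resection, which is standard care. Two routes are not: excision after withdrawal or an adverse event (4.4.1), and the small operation with local anesthetic when surgery is unnecessary or delayed past 52 weeks (5.2.4).

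**How many gates are affected.** Section 3.1 sets two three-patient gates in Phase 1A and two in Phase 1B: 2 + 2 = 4. Section 1.6.2 reports both Phase 1A cohorts as followed past explantation without unacceptable toxicity, which leaves at most 4 − 2 = 2. Section 8.4 applies to every remaining patient in either phase.

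**The case against.** Much can be said for the plan.

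- A reader might infer that a placement-caused grade 3+ event would not halt the study, or that halting is discretionary. The documents do not support that. The stop in 8.4 has no attribution filter and is broader than the endpoint. Only the test for lifting it is narrow.
- A reader might also infer that such events go uncounted. They do not: 3.2 records them regardless.
- The protocol sometimes uses OxyChip safety to include placing it. The Phase 1A schema describes the primary endpoint as the safety of placement and removal, and its note on oxygen measurements speaks of unexpected device events from implanting the chip. On that reading 8.4 already covers placement. This stands as a possible reading. It competes with the passages that separate the two, and it does not reach fiducials.
- Section 7.1 refers back to 3.1, whose Phase 1A gates are broader. This stands, so for Phase 1A the fault is inconsistency between sections and not missing cover.
- Section 1.6.1 introduces Phase 1B as a similar design to Phase 1A, which arguably carries over a criterion with no attribution limit. This narrows the Phase 1B gap but leaves the reader to infer the rule.
- Section 1.5.5 says the FDA's Phase 1 safety and efficacy requirement has been met, so the Phase 1B gates may already have been passed. The available text does not settle this. It does not affect 8.4.
- The Data Safety Monitoring and Accrual Committee can suspend the study (10.1). That is a real safeguard, but it is discretion, not a stated criterion.

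**Conclusion.** The mismatch is in the text. It matters mainly for the 8.4 re-opening test and, secondarily, for the Phase 1B gates if they are still open. It calls for an inexpensive alignment of wording and does not show that patients have been put at risk: the highest toxicity grade reported to date is 1.

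Its practical frequency cannot be estimated from the documents, which give no rate of procedure-caused grade 3+ events. The conclusion rests on a literal reading in which the OxyChip means the implanted piece. If the sponsor intends the term to include placement, the needle-placement part of the gap closes, but fiducials would still need to be named and study-specific removal would still need to be made explicit.

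**What to change.** **Section 8.4.** State that the study stays closed until the event is judged unrelated to any of the following: the OxyChip, the fiducials, the implantation procedure, a study-specific removal procedure, or the oxygen measurements. Exclude complications of the standard-of-care resection.

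**Section 7.1.** Base progression on any grade 3+ toxicity attributed to the device or procedure as in 3.2, expected or not, together with other unexpected adverse events attributed to either. The Study Summary's expansion wording should follow 7.1.

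**Cost.** A few sentences of amendment and an occasional longer hold. There is one consequence to accept knowingly: 8.4 offers no way to re-open after a related event, so under the revised wording a procedure-caused event would also keep the study closed unless the protocol is amended. Section 1.6.1 expects procedures to be modified as experience grows, so the sponsor may wish to add a route for re-opening after correction and review by the monitoring committee and the IRB. That is a separate design choice for the sponsor, and the alignment does not depend on it.

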## 3 Study Design

### 3.1 General Design

This is a Phase 1 clinical trial. Total enrollment will be 60 evaluable patients. Evaluable patients will be defined as patients who have the OxyChip implantation for the minimum of 3 days.

The study is split into Phase 1A (shorter duration of implantation with no other cancer therapy planned prior to excision) and Phase 1B (longer duration of implantation that is typically up to 12 weeks while receiving radiation therapy or longer if receiving neoadjuvant chemotherapy prior to surgical excision), as described below. OxyChip implant duration for both phases can be extended to 52 weeks (excluding the initial 6 evaluable patients in Phase 1A which may have the OxyChip implanted up to 4 weeks).

[figure not shown]
The initial 6 evaluable patients in Phase 1A will have the OxyChip placed for a short duration (up to 4 weeks) after which the OxyChip will be removed when the tumor mass is resected, prior to delivery of any further therapies. After successful implantation and removal of the OxyChip without any unacceptable toxicity in the first 6 evaluable patients, the Phase 1A cohort will be expanded to a total of 30 patients. In order to complete the safety and toxicity assessment of the short-term implantations, we will require that at least 3 patients have OxyChip implantations for a duration of at least 2 weeks, prior to proceeding to Phase 1B (long term implantation). This may require enrollment of additional patients in Phase 1A in order to meet this criterion. Phase 1B will consist of one cohort of 3 evaluable patients receiving chemotherapy treatment and one cohort of 3 evaluable patients receiving radiotherapy. Only after a full evaluation of the first 3 patients that underwent chemotherapy will additional patients receiving chemotherapy be enrolled. Similarly, only after a full evaluation of the first 3 patients that underwent radiotherapy will additional patients receiving radiotherapy be enrolled. The two cohorts of 3 patients in Phase 1B are independent of each other, so either of these cohorts may continue accrual after the initial 3 patients while the other is still accruing for the initial 3 patients. A total of 30 patients will be enrolled in Phase 1B. .

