Patient population	
There will be a total of 30 patients enrolled in Phase 1A.
 
Initially, 3 patients will be enrolled; the OxyChip will be placed; physical examination of the site will be made periodically (at least in conjunction with visits where oxygen measurements will be made) starting from one day following implantation for up to 52 weeks – at which point the tumor will be resected with concurrent removal of the OxyChip. If no adverse events are noted in the physical exams or tissue pathology, an additional 3 patients will be enrolled in this phase of the study. The decision to start the second cohort of 3 will be made by the study PI after review of surgical pathology reports and after the first 3 evaluable patients are at a time point more than 2 weeks following surgical removal of the OxyChip. Next, if no unacceptable toxicity is noted after completion of the first 6 patients, the enrollment will be open to 24 more, for a total of 30 patients. (Note: the enrollment totals will include patients enrolled at DHMC or Emory University, once the addition of Emory as a participating site is approved.)
 
In addition the following eligibility and exclusion criteria will apply:
 
 
• Superficial tumors located <math>\leq 3</math> cm from skin or mucosal surface.
 
• Surgical resection of the tumor is planned at least 3 days following implantation.
 
• Eligible tumors for this phase of the protocol are any tumors that (a) are identified by imaging or physical exam to be superficial enough for OxyChip placement and (b) will receive surgical resection with intent to remove the entire tumor.
 

	
 
• Previous radiation to the site is not allowed.
 
• Planned use of chemotherapy or radiation therapy or use of angiogenesis inhibitor prior to resection is not allowed.
 
• Patients do not have to agree to an oxygen measurement in order to be eligible. Although oxygen measurements are desirable, the primary endpoint is safety of the OxyChip placement and removal over a short time frame.
 
• Tumors must be <math>\geq 2.5</math> cm in minimum diameter to be eligible.
 

OxyChip placement	Placement of OxyChip will be through a minimally invasive procedure (see methods for implantation protocol ).

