### **3.3 Secondary Study Endpoint**

*For the secondary objective (feasibility of repeated oxygen measurements in tumors using the OxyChip and EPR oximetry) the secondary endpoint is completion of planned oxygen measurements.*

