### **5.3 Subject Compliance Monitoring**

Patients in Phase 1A will typically have the OxyChip implanted for a short duration ( $\leq 4$  weeks), but may remain for up to 52 weeks, and the patient will be seeing the surgeon for surgical planning and post-operative evaluations, making non-compliance unlikely. Phase 1A patients will be evaluated at least monthly prior to the OxyChip removal to check for any adverse events, as per the primary objective. Patients in Phase 1B will be receiving daily radiotherapy or a course of chemotherapy and therefore will be seen by a physician at least weekly or with each chemotherapy cycle for standard evaluation. At these appointments, the PI, co-investigators or staff protocol members perform safety monitoring by querying the patient about his or her local symptoms relating to the OxyChip implantation, and by inspection of the implantation site if possible, depending on the patient's willingness to allow inspection. Evaluation can also be performed at Norris Cotton Cancer Center North by one of the DH radiation or medical oncologists who are protocol staff, if the patients elects to receive radiation or chemotherapy at that facility prior to surgery (Phase 1B).

If the patient is unwilling to see the PI or co-investigators during a visit at which toxicity is to be assessed, or if the patient is unable to be seen due to logistical considerations, the patient by phone to evaluate potential toxicity. All efforts will be made to see the patient in clinic and perform an inspection of the implanted site. If the patient is receiving oxygen measurements, the patient will be seen by the EPR team at that time, ensuring compliance. It is possible that patients will decline oxygen measurements, but this will have a minor impact on the secondary objective (feasibility), and no impact on the primary objective (safety). Assessments by non-study physicians as part of standard of care are also an acceptable replacement if the patient is not accessible for an in-person evaluation.

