## 7.2 Subject Population(s) for Analysis

The subject populations whose data will be subjected to analysis (both primary and secondary) include all evaluable participants in this Phase I trial.

---

 US Dept of Health and Human Services, Food and Drug Administration Center for Devices and Radiological Health. Center for Biologics Evaluation and Research. "Investigational Device Exemptions (IDEs) for Early Feasibility Medical Device Clinical Studies, including Certain First in Human (FIH) Studies: Guidance for Industry and Food and Drug Administration Staff". Document issued October 1, 2013.  
<http://www.fda.gov/MedicalDevices/DeviceRegulationandGuidance/HowtoMarketYourDevice/InvestigationalDeviceExemptionIDE/ucm162453.htm>.

Browne RH: On the use of a pilot sample for sample size determination. *Stat Med.* 1995, 14: 1933-1940.

Sim J, Lewis M: The size of a pilot study for a clinical trial should be calculated in relation to considerations of precision and efficiency. *J Clin Epidemiol.* 2012, 65: 301-308.

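### Section 7.1 does not analyse the Section 3.3 secondary endpoint (completing the planned oximetry measurements), and Phase 1B on treatment has no planned number to complete

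*Combined protocol and SAP*

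**What the plan says.** - **Endpoint (3.3).** "the secondary endpoint is completion of planned oxygen measurements". No unit, denominator or target is attached.
- **Analysis (7.1).** For the feasibility goal, "we will use a qualitative assessment about whether any attempted measurements were successful, and assess the time for making measurements". The paired t-test, ANOVA, nonlinear fitting and mixed models that follow are all about pO2 values.
- **Population (7.2).** Primary and secondary analyses "include all evaluable participants in this Phase I trial". Section 3.1 adds: "Evaluable patients will be defined as patients who have the OxyChip implantation for the minimum of 3 days". Having a measurement is not part of that definition.
- **Measurement is optional (3.1 schema, both phases).** "Patients do not have to agree to an oxygen measurement in order to be eligible". Section 5.3 foresees refusals and expects them to matter little for feasibility, but gives no rule for counting them.
- **Planned numbers (3.1 and schema).** The goal is at least 2 measurements between placement and removal in Phase 1A, and at least 2 before radiation in Phase 1B. On treatment, Phase 1B has only a maximum of five a week. No pre-treatment number is given for chemotherapy patients.
- **Session content (5.2.2).** A patient unwilling to breathe oxygen gives baseline data only, and any session may be ended early.
- **Failures so far (1.5.3).** In some patients no signal was found. Their chips lay 10 to 16 mm deep, while tumors up to 3 cm from the surface are eligible (4.1).

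**The concern.** The endpoint counts what was planned; the analysis looks at what was attempted. A patient who declines every session belongs to the 7.2 population but never enters the attempted set. The quantity in 7.1 can therefore look better than the one in 3.3, and nothing in 7.1 leads back to completion.

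At stake is how the feasibility result is used. The objective in 2.2 is *repeated* measurement, and 7.1 says the study should help design a larger one. If the denominator, the Phase 1B target and the meaning of a completed session are left open, they will be settled after the results are known.

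**Working it through.** The plan gives no completion rate, target or power for this endpoint, so there is no figure to reproduce. The check is a comparison of sections, with arithmetic to show size.

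**1. What 7.1 would produce.** It yields a qualitative statement about attempts, a summary of session times, and pO2 analyses. None of these is a count or proportion of planned measurements completed.

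**2. Effect of the denominator in Phase 1A.** The planned size is 30: "There will be a total of 30 patients enrolled in Phase 1A". Suppose d evaluable patients decline and all others complete at least 2. Completion is (30 − d)/30 among all evaluable patients and (30 − d)/(30 − d) among those who agreed. The values of d are assumptions. Intervals are exact (Clopper-Pearson) 95%; when all n complete, the lower limit is 0.025^(1/n).

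| d | All evaluable | Agreed to measurement |
|---|---|---|
| 0 | 30/30 = 100% (88.4% to 100%) | the same |
| 3 | 27/30 = 90% (73.5% to 97.9%) | 27/27 = 100% (87.2% to 100%) |
| 6 | 24/30 = 80% (61.4% to 92.3%) | 24/24 = 100% (85.8% to 100%) |

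Each decliner moves the first column by 1/30 = 3.3 percentage points and leaves the second at 100%. The interval is widest at 15/30: 31.3% to 68.7%.

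**3. Phase 1B before radiation.** The goal of at least 2 is countable, but n is not known. The phase total is 30 in Section 3.1 ("A total of 30 patients will be enrolled in Phase 1B") and at most 30 in the Study Summary. The split between radiotherapy and chemotherapy is not fixed. If the total is 30 and each starting cohort of 3 fills, radiotherapy could have 3 to 27 patients. If all completed, the lower limit would run from 0.025^(1/3) = 29% to 0.025^(1/27) = 87%. The n = 30 intervals should not be carried over.

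**4. Phase 1B on treatment.** A ceiling of five a week over the 5-week radiotherapy course (5.2.4) permits 0 to 5 × 5 = 25 sessions. Take, as an illustration only, a patient with 5 sessions. Against an assumed plan of one a week, completion is 5/5 = 100%. Against five a week it is 5/25 = 20%. The documents do not choose between these, so the rate is undefined.

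**5. Minor related point: pO2 averaging.** Section 7.1 averages pO2 across visit days per subject. For a radiotherapy patient with exactly 2 pre-radiation readings (the goal is a minimum, so this is one case), those readings carry 2/(2 + 5) = 29% of the average at one on-treatment reading a week for 5 weeks, and 2/(2 + 25) = 7% at five. The average thus mixes two periods in proportions set by visit frequency, although 2.2 asks for levels during therapy.

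**The case against.** **It is a pilot, and feasibility gates nothing.** Cohort progression depends on adverse events (7.1) and stopping on toxicity (8.4). This is right and limits the consequence. A qualitative assessment is acceptable in a pilot, but this one is not an assessment of the endpoint defined in 3.3.

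***Any* may not mean *at least one*.** A reader might infer that a single success would pass the study as feasible. The text does not support that: 7.1 sets no threshold, and the word can equally mean *which of the attempts*. The fair criticism is that 7.1 is vague and counts attempts.

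**Decliners may have nothing planned.** A reader might infer that every decliner is a non-completer. The protocol does not say so. Measurement is optional by design, and 5.3 expects little effect from refusals. What stands is that no counting rule is given, so both denominators should be shown.

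**Visit-level data are kept.** The ANOVA in 7.1 compares time periods per visit, and mixed models are named. It would be wrong to say that visit-level information is discarded. Only the single per-subject average is at issue, and it is a small matter.

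**The counts can be recovered.** Largely true: 5.2.2 records the time of each reading, 4.4.1 tracks reasons for patient-requested stopping, and 9.3 requires missing data to be explained. That preserves the data; it does not fix the definitions in advance.

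**Conclusion.** The mismatch between 3.3 and 7.1 is certain on the text: the stated secondary endpoint has no analysis. Completion can be computed for Phase 1A and for Phase 1B before radiation, where a goal of at least 2 exists. It cannot be computed for Phase 1B on treatment.

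The size depends on how many patients decline or give no signal, which the available text does not state. In Phase 1A the gap between the two denominators is 3.3 points per decliner if all others complete. The numbers of decliners, the 5-session patient, the one-a-week plan and the 2/7 and 2/27 weights are illustrative assumptions.

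A reader might also infer that correcting 7.1 now would make the whole feasibility result pre-specified. It would not: more than 60 measurements had already been made when this version was written (1.5.3). The primary safety objective and cohort progression are untouched. This should be corrected, but it does not threaten the trial.

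**What to change.** In Section 7.1:

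1. For Phase 1A, and for Phase 1B radiotherapy patients before radiation, report the number and proportion of evaluable patients with at least 2 completed measurements. Give an exact 95% CI based on the actual cohort size. Show the result among all evaluable patients and among those who agreed to measurement.
2. Report success among attempted sessions separately, with patients who declined, who stopped and who gave no signal in separate rows.
3. Reconcile 3.1, 3.3 and 7.1. The sponsor states the Phase 1B on-treatment denominator and what counts as a completed session (for example, whether a baseline-only or shortened one does), and clarifies whether a pre-treatment goal is meant for chemotherapy patients. Otherwise, on-treatment sessions are reported descriptively. No schedule is proposed here.
4. Say in the report that these definitions were set after part of the data had been collected.
5. Minor: summarise Phase 1B pre-treatment and on-treatment pO2 separately.

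**Cost.** Wording in 7.1, the sponsor's decisions in item 3, and perhaps one CRF field for declined and no-signal patients, since 4.4.1 covers only stopping at the patient's request. The feasibility figure may look less favourable. No new visits or procedures are needed.
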